10.4.3 Analysis of the Secondary Endpoint(s)

Seizure frequency will be analyzed on a relative scale, examining the hypothesized percental decrease in number of seizures from baseline to week 4. For this purpose, the log-transformed data will be analyzed and the resulting point estimates and 95% confidence limits from the Wilcoxon signed-rank test will be converted back to the original scale.

10.4.4 Safety Analyses

See Analysis of Primary Endpoint (Section 10.4.2)

10.4.5 Adherence and Retention Analyses

We do not foresee any major problem with missing values. Study drop-out will be examined by interviews of the study participants (see section "Participant Withdrawal or termination") and the reasons for drop-out will be

tabulated. If drop-outs occur due to tolerability or perceived side effects this information will be integrated into the safety analysis.

10.4.6 Baseline Descriptive Statistics

Demographic data and baseline characteristics will be presented using descriptive statistics (e.g. Number of observations, Number of missing values, Mean, Median, 1st and 3rd quartiles, Minimum and maximum values, Standard deviation).

10.4.7 Planned Interim Analyses

No interim analysis is planned. An independent DSMB will review safety data on an ongoing basis.

10.4.9 Multiple Comparison/Multiplicity

No adjustments for multiplicity of statistical tests are planned.

10.4.10 Tabulation of Individual Response Data

All individual data will be tabulated in listings and will be described in detail in the SAP.

10.5 Sample Size

The sample size was not based on any statistical criteria but what was pragmatic and achievable, given that PMS is a rare disease. See section "Strategies for Recruitment and Retention".

10.6 Measures to Minimize Bias

Subjects will be recruited on the basis of the genetic diagnosis of PMS and epilepsy. There will otherwise be no selection bias and we anticipate a random sampling of participants within the age range and within the predefined severity level of seizures.

10.6.1 Enrollment/ Randomization/ Masking Procedures

Not Applicable

10.6.2 Evaluation of Success of Blinding

Not Applicable

10.6.3 Breaking the Study Blind/Participant Code

Not Applicable

11 SOURCE DOCUMENTS AND ACCESS TO SOURCE DATA/DOCUMENTS

Source documents will be hard copies of the case report forms (CRFs) that will be entered into an electronic database. Source documents will be stored securely in accordance with GCP and the electronic database is password protected on a secure server. All data from source documents will be double entered to ensure fidelity within the electronic database. Access to source documents and the electronic database will be limited to authorized individuals (according to 21 CFR 11.10(d)). Each user of the electronic database will have an individual account. The user will log into that account at the beginning of a data entry session, input information (including changes) on the electronic record, and log out at the completion of data entry session. Authorized individuals will work only under their own password and will not share the password with others and will not login on behalf of others. When someone leaves a workstation, the authorized individual will log off and automatic log off will be triggered after idle periods in addition to an automatic screen saver to prevent data entry until a password is entered.

12 QUALITY ASSURANCE AND QUALITY CONTROL

Data will be collected on CRFs or parent self-report surveys and uploaded in double-entered fashion to a secure electronic database. Hard copy records will be stored at a secure location in locked cabinets within locked offices. Electrophysiological and eye tracking data will be automatically recorded in electronic format and subsequently entered into the database. Backup and recovery procedures will protect against data loss and records will be regularly backed up to prevent loss and ensure the quality and integrity of the data. Backup and recovery logs will be maintained to facilitate an assessment of the nature and scope of data loss in case of a system failure.

13 ETHICS/PROTECTION OF HUMAN SUBJECTS

13.1 Ethical Standard

The study will be conducted according to Good Clinical Practice (GCP), the 1996 Declaration of Helsinki (Protocol Appendix A), (US 21 CFR Part 50—Protection of Human Subjects, and Park 56—Institutional Review Boards) and local rules and regulations of the country.

13.2 Institutional Review Board

The study will be reviewed and approved by the appropriate Program for the Protection of Human Subjects, the Investigational Research Pharmacy, and by the General Clinical Research Center as indicated.

13.3 Informed Consent Process

13.3.1 Consent/assent and Other Informational Documents Provided to Participants

The investigator will describe the protocol to potential subjects' parents/guardians in person, although general information and assessment for eligibility can be carried out by phone if necessary. Each subject's signed informed consent form will be kept on file by the investigator for possible inspection by regulatory authorities. The parents/guardians will receive a copy of the signed and dated written informed consent form and any other written information provided to the subjects' parents/guardians, and will receive copies of any signed and dated consent form updates. Any amendments to the written information will be provided to subjects' parents/guardians.

13.3.2 Consent Procedures and Documentation

The Informed Consent may be read to the subjects' parent/guardians, but, in any event, the investigator or designee shall give the subjects' parents/guardians ample opportunity to inquire about details of the study and ask any questions before dating and signing the Informed Consent Form. The Informed Consent will be created with a level of language fully comprehensible to the prospective subjects' parents/guardians. Informed consent will be documented by the use of a written consent form approved by the IRB and signed and dated by the subjects' parents/guardians and by the person who conducted the informed consent discussion. The signature confirms the consent is based on information that has been understood.

13.4 Participant and Data Confidentiality

13.4.1 Research Use of Stored Human Samples, Specimens or Data

A subject identification code will be used in lieu of the subject's name on all study data compiled and delivered to the designated data collection center. All source documents and study data will be kept confidential, in accordance with all requirements of the laws.

13.5 Future Use of Stored Specimens

Not Applicable Study ID: AMO-01

14 DATA HANDLING AND RECORD KEEPING

14.1 Data Collection and Management Responsibilities

Upon signing informed consent, all subjects will be assigned a unique identification and only the principal investigator and authorized personnel will have access to a password protected linking document stored on a secure server. Data will be collected on case report forms (CRFs) with assigned IDs and entered into a deidentified database on a secure server. Informed consent and clinical documents will be stored separately. All non-electronic data will be stored in locked file cabinets contained within locked offices. All electronic data will be stored secured server. The investigator is responsible for all aspects of the conduct of the study at their respective site. These would include: the dispensing and the administration of the investigational product, the implementation of the study protocol, the collection and reporting of the study data and the protection of the health and welfare of the personnel involved in the study during the study.

14.2 Study Records Retention

Study records will be retained for a period of at least 2 years following the date a marketing application is approved for AMO-01 in PMS. If no application is filed or if the application is not approved for such indication, records will be retained until 2 years after the investigation is discontinued and FDA is notified.

14.3 Protocol Deviations

Protocol deviations will be reported to the sponsor and to the IRB and documented in a note to file in the patients case report form.

14.4 Publication and Data Sharing Policy

The investigators are committed to collaborate and share data freely with other investigators. Our institution sponsors well established resources for the identification, evaluation and distribution of research tools developed with federal grant funding. The research team is committed to an open model of scientific sharing. The investigators will comply with the standard Resource Sharing Plans. We routinely disseminate our scientific discoveries through the publication of peer-reviewed manuscripts in journals, at scientific conferences. through the internet http://www.shank3gene.org/: and (e.g. https://www.rarediseasesnetwork.org/cms/DSC; http://22q13.org/j15/). Any advances that result from the proposed studies may be disseminated to the broadest community through patent protection and commercialization. We will continue to utilize these approaches to have a broad impact upon the research community and the patients who directly benefit from this treatment development.

16 CONFLICT OF INTEREST POLICY

The Conflicts of Interest Office (COI) at Icahn School of Medicine was established in 2009 and is located in the Office of the Dean. The COI Office helps to oversee Icahn School of Medicine at Mount Sinai's efforts to identify and manage potential conflicts of interest. The school encourages collaborative relationships with industry that could lead to breakthroughs in research and clinical care, and it is essential that these relationships are free of real or perceived conflicts. The COI Office educates faculty, staff and trainees about Icahn School of Medicine at Mount Sinai's COI policies, both institutional and research-specific, and provides guidance in the disclosure of financial interests. We also are responsible for institutional compliance with regulatory requirements relating to conflicts of interest. All of these components are essential to creating an environment of transparency for our relationships Form to disclose all financial interests that investigators have outside of their employment at Mount Sinai. In addition, a Financial Interests in Research Disclosure Form is completed with each grant submission and annual continuation to determine whether any of the financial conflicts of interest pose actual or perceived conflicts with a proposed research project.

TCH and Baylor College of Medicine (BCM) require all Investigators to report Significant Financial Interests (SFIs) that reasonably appear to be related to the investigator's Institutional Responsibilities. BCM must review the matter and determine if an Investigator's Significant Financial Interest is related to the research, and if the research-related Significant Financial Interest is a Financial Conflict of Interest that should be managed, reduced or eliminated. Special precautions must be taken to avoid perceived or actual bias with respect to research involving human subjects that encompasses the evaluation of strategies or products that may affect or be affected by the financial interests of BCM or BCM Investigators. A BCM Investigator shall not ordinarily participate in any Research involving human subjects that encompasses evaluation of such a strategy or product if he/she has a Significant Financial Interest that could directly affect the design, conduct or reporting of the Research unless he/she presents a compelling justification for a waiver of this policy based on his/her unique qualifications as an Investigator. The degree of risk to human subjects and the compelling justification will be reviewed by the Research Conflict of Interest Committee (RCOIC). If compelling circumstances are found, the Research will be subject to stringent management measures to ensure the safety of the human participants and the integrity of the Research. The IRB must review and approve any management plan for human subject Research. The IRB may require additional safeguards to protect human subject participants in addition to those required by the RCOIC.

APPENDIX A: Clinician-Completed PMS Domain-Specific Causes for Concern VAS

Date

ID _____ Evaluator Signature _____

Phelan-McDermid Syndrome Specific Concerns – Clinician

Please rate the areas of concern that are priority targets for change during treatment in the categories below. Your choices should be associated with the patient's Phelan-McDermid Syndrome. You can select any sign or symptom fitting the category.

1. Speech and language difficulties
The sign or symptom causing concern is:
How severe has the sign or symptom been in the past week? Place a vertical mark on the line below to indicate how bad you think the sign or symptom has been in the last week.
Completely Absent Very Severe
2. Problems with thinking and learning
The sign or symptom causing concern is:
How severe has the sign or symptom been in the past week? Place a vertical mark on the line below to indicate how bad you think the sign or symptom has been in the last week.
Completely Absent Very Severe
3. Seizures
The sign or symptom causing concern is:
How severe has the sign or symptom been in the past week? Place a vertical mark on the line below to indicate how bad you think the sign or symptom has been in the last week.
Completely Absent Very Severe

Date _____ ID _____

Evaluator Signature

Phelan-McDermid Syndrome Specific Concerns – Clinician

Please rate the areas of concern that are priority targets for change during treatment in the categories below. Your choices should be associated with the patient's Phelan-McDermid Syndrome. You can select any sign or symptom fitting the category.

4. Problems with gross motor functioning
The sign or symptom causing concern is:
How severe has the sign or symptom been in the past week? Place a vertical mark on the line below to
indicate how bad you think the sign or symptom has been in the last week.
Completely Absent Very Severe
5. Destricte d'internets en d'au son stitions hab enions
5. Restricted interests and/or repetitive behaviors
The sign or symptom causing concern is:
How servers has the size or comptem been in the part week? Diago a vertical mark on the line below to
How severe has the sign or symptom been in the past week? Place a vertical mark on the line below to indicate how bad you think the sign or symptom has been in the last week.
Completely Absent Very Severe
6. Social communication problems
The sign or symptom causing concern is:
The sign of symptom causing concern is.
How severe has the sign or symptom been in the past week? Place a vertical mark on the line below to
indicate how bad you think the sign or symptom has been in the last week.
Completely Absent Very Severe

Date _____ ID _____

Evaluator Signature

Phelan-McDermid Syndrome Specific Concerns – Clinician

Please rate the areas of concern that are priority targets for change during treatment in the categories below. Your choices should be associated with the patient's Phelan-McDermid Syndrome. You can select any sign or symptom fitting the category.

7. Sensory sensitivities
The sign or symptom causing concern is:
How severe has the sign or symptom been in the past week? Place a vertical mark on the line below to indicate how bad you think the sign or symptom has been in the last week.
Completely Absent Very Severe
Completely Assent very Severe
8. Activities of daily living
The sign or symptom causing concern is:
How severe has the sign or symptom been in the past week? Place a vertical mark on the line below to indicate how bad you think the sign or symptom has been in the last week.
indicate now bad you mink the sign of symptom has been in the fast week.
Completely Absent Very Severe
9. Sleep disturbance
The sign or symptom causing concern is:
Here serves has the size of server have in the next model. Discuss excitical mode of the line halom to
How severe has the sign or symptom been in the past week? Place a vertical mark on the line below to indicate how bad you think the sign or symptom has been in the last week.
1
Completely Absent Very Severe

APPENDIX B: Caregiver Completed Seizure Diary

INSTRUCTIONS: Enter the Month and Year on the line where indicated. The days of the month are already entered on each line of the log. Please enter seizure information in your diary each day. For each day that a seizure occurred enter in the code and number of seizures that occurred as demonstrated in part A. If a new type of seizure occurs, describe it. If a code has been specified for a type of seizure, please make sure to keep the same code for the same type of seizure at the following visits. Use a new code for a new type of seizure. If no seizures occurred, please check the box where indicated. Please leave the last two columns (seizure code and number of seizures of each type) blank.

A.

Example: Seizure Description	Sample Code Defined
Left Arm Jerking	by Study Doctor
I pass out; my whole body starts to jerk	А
	В

Enter Description of your Seizure	Codes to be defined by your Study Doctor
•	Code
•	Code
•	Code
	Code
•	Code
	Code
•	
•	Code

В.

To be completed by parent			To be completed by study staff	
Date:	Please check the box below if NO seizure occurred on this day	 Patient Description of Seizures If new seizure type, enter description Example: If you had 2 code A seizures you would enter A:2 	Seizure Code	Number of Seizures of Each Type
 				

To be completed by parent			To be completed by study staff	
Date:	Please check the box below if NO seizure occurred on this day	 Patient Description of Seizures If new seizure type, enter description Example: If you had 2 code A seizures you would enter A:2 	Seizure Code	Number of Seizures of Each Type

APPENDIX C: Syndrome Specific Clinical Global Impressions- Severity and Improvement

CGI-S and CGI-I

The Clinical Global Impression – Severity of Illness (CGI-S) and Clinical Global Impression – Improvement of Illness (CGI-I) are brief, easy to administer, clinician-rated measures (Guy, 1976). The CGI-S asks the clinician to rate the patient's current severity of illness based on the clinician's total clinical experience with the relevant population. The CGI-S is rated on a 7-point scale, with a range of responses from 1 (normal, not at all ill) through 7 (amongst the most extremely ill patients). The CGI-I asks the clinician to rate the patients' total improvement since baseline, whether or not the improvement is judged to be due entirely to the experimental treatment. The CGI-I is rated on a 7-point scale, with a range of responses from 1 (very much improved) to 7 (very much worse). For both the CGI-S and the CGI-I, the clinician is allowed to use all available information at the time of the rating.

The CGI-I has emerged as a convention for bifurcating clinical trial subjects into "responders" and "non-responders". In this application, the CGI-I can be a useful tool for gaining a general overview of the therapeutic potential of an experimental treatment. One of the relative detriments of both the CGI-S and –I is the lack of the measures' assessment of specific sign or symptoms associated with the disorder under study (Busner et al., 2009). An approach that has been developed to enhance the precision and clinical meaningfulness of CGI ratings is to utilize anchor points that are specific to the signs and symptoms of the disorder under study.

References:

Guy W (1976). Clinical global impressions. In: Guy W, editor. ECDEU assessment manual for psychopharmacology (Revised). Rockville, Maryland, National Institute of Mental Health: 217-221.

Clinical Global Impression – Severity of Illness Scale (CGI-S):

"Considering your total clinical experience with PMS patients, how severely ill is this patient at this time?"

- 1- Normal, not at all ill: The patient is indistinguishable from other individuals that do not have PMS. The patient has no overt PMS symptoms and no persistent dysfunction in the wake of having been diagnosed with PMS.
- 2- Borderline ill: The patient has very occasional PMS symptoms that seem modestly excessive in intensity, frequency or duration compared to individuals that have not been diagnosed with PMS. These symptoms have only a transient impact on functioning, with no need for any special intervention.
- 3- Mildly ill: The patient has occasional PMS symptoms that seem modestly excessive in intensity or duration, or the patient experiences very occasional PMS symptoms that are modestly excessive both in intensity and duration as compared to individuals without a PMS diagnosis. These symptoms have a limited impact on the patient's functioning, generally only in one setting, and require that others make some adjustments or accommodations in interacting with this patient.
- 4- Moderately ill: This PMS patient is clearly distinguishable from other individuals because of his/her PMS symptoms and the impairment that they cause. The patient's PMS symptoms are clearly excessive in frequency, intensity or duration compared to others that have not received a PMS diagnosis, and have limited impact on the patient's functioning in multiple settings or moderate impact in one setting. Caregivers, family members, teachers and co-workers make adjustments when interacting with this patient to avoid exacerbation of his/her symptoms and to deal with them when they occur.
- 5- Markedly ill: This patient's PMS symptoms occur frequently and are noticeable in intensity or duration to even casual observers or occur infrequently but are quite intense or long-lasting. There is moderate impact on the patient's functioning in multiple settings or extreme impact in one setting. Caregivers, family members, teachers and co-workers utilize interventions that are necessary in order to deal with this patient's symptoms. Special accommodations related specifically to the patient's PMS symptoms are likely necessary at home, at school or in the workplace.
- 6- Severely ill: The patient's PMS symptoms occur very frequently and are noticeable in intensity or duration to even casual observers or occur infrequently but are severely intense or extremely long-lasting. Often there is marked impairment of normal day-to-day capabilities or skills necessary to function at school or in the workplace. Multiple interventions are required to address the patient's PMS symptoms to minimize consequences.
- 7- Among the most extremely ill patients: The patient's PMS symptoms occur the majority of the time and are very disruptive to functioning in multiple areas. There are very few times, if any, of normal functioning. There are often serious concerns about the patient's ability to provide adequate care for him/herself as a consequence of the PMS symptoms. The patient requires almost constant monitoring by caregivers or others.

bject ID:	Study ID:
(Clinical Global Impression- Severity of Illness Scale (CGI-S)
Date of	Assessment
	ring your total clinical experience with Phelan McDermid Syndrome patients, how / ill is this patient at this time?
	1- Normal, not at all ill
	2- Borderline ill
	3- Mildly ill
	4- Moderately ill 5- Markedly ill
	6- Severely ill
	7- Among the most extremely ill patients
	· · · · · · · · · · · · · · · · · · ·
Score	
Evaluato	or Name
Evaluato	or signature
Date	
1	

CGI—Improvement – A User's Guide

1. Very Much Improved designates marked improvement, across settings and/or across multiple problem areas. Although a CGI-I of 1 does not strictly require that the patient qualify for a CGI-S rating better than baseline, usually the CGI-S does also improve. Such improvement must be very substantial and is usually accompanied by considerable patient and/or caregiver enthusiasm. Such patients are usually noticeably improved in the clinic as well.

2. Much Improved may denote moderate improvement in a single symptom area, especially if seen across settings. Likewise, moderate improvements in several areas, even if confined to one setting, may warrant a rating of "Much improved." Durability of the change should be taken into account. For example, a change reported for the last few hours probably would not warrant such a rating. On the other hand, a change that was clearly in evidence for the last several days or longer probably would warrant a rating of 2. It is not necessary that the patient qualify for a CGI-S rating better than baseline to receive a CGI—I rating of 2, but often (not always) the CGI-S also improves.

3. Minimal Improvement indicates modest improvements, especially if confined to one setting. Trivial changes or changes that are possibly present or require guesswork usually would be scored as 4 (the level below this one).

4. No Change indicates, by definition, the absence of change in behavior or clinical presentation from baseline to subsequent assessments. Chance fluctuations and equivocal improvements or declines should be included here.

5. *Minimally Worse* indicates some worsening in symptoms that are mild to moderate or may be confined to one setting.

6. Much Worse designates moderate to moderately serve worsening. This may include moderate levels of worsening in a single symptom area when observed across settings. Moderately severe changes that are confined to one setting may warrant a rating of "Much Worse."

7. Very Much Worse designates significant worsening, across settings and/or across multiple symptoms.

N.B. The CGI-I is a rating of *change*; normalization is not necessary for a rating of 1, although if the clinical presentation is unequivocally improved and is evident across settings, it suggests an Improvement score of 1. A CGI-I of 2 is appropriate for definite, unequivocal improvement of a magnitude that makes the clinician confident that the treatment is helping. An improvement score of 3 (or 5) is appropriate if variations in ratings and other criteria appear to represent more than random chance or rating error, but are not definite and unequivocal. A score of 4 is appropriate for slight variation in either direction of a magnitude that is likely due to chance, natural history, external events, or rating error.

~	й I.	5 35	1.00
Su	b	ject	D:

Study ID:

Clinical Global Impression- Improvement Scale (CGI-I)
Date of Assessment
Compared to the baseline assessment in this study, if you consider the signs and symptoms associated with this patient's Phelan McDermid Syndrome, how much has he/she changed? Rate his/her total improvement whether or not, in your judgement, it is due entirely to the study drug.
 Very much improved Much improved Minimally improved No change Minimally worse Much worse
7- Very much worse Score
Evaluator Name
Evaluator signature
Date

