4.1 Description of the Study Design

This is an open-label study to investigate the safety, tolerability and efficacy of a single 6-hour intravenous infusion of AMO-01 to treat adolescents and adults with PMS and co-morbid epilepsy. The subjects in this study will be administered the experimental study medication and then be followed up to ascertain safety and tolerability, and to determine whether their seizure frequency, as well as their signs and symptoms of PMS, are improving, using a caregiver-completed seizure diary as well as accepted rating scales and functional measures in addition to clinical EEG. Approximately 15 subjects will be screened and up to 10 subjects will receive study medication.

The study will have 4 phases (Figure 1, Study Design):

- Screening (Weeks -4 to -1): Subjects will be screened to ensure adherence to eligibility criteria and to assess pre-medication seizure frequency
- Baseline (Day 0): Subjects will complete baseline assessments in-clinic prior to study drug administration
- Study Drug Administration (Day 0): Eligible subjects will receive a single 6-hour intravenous infusion at a single dose of 120 mg/m²
- Follow-up (+1 day Week 8): follow-up visits will occur at 1 day after and 1, 2 and 4 weeks after receiving study medication. A phone call will occur 8 weeks after receiving study medication.

• .

Figure 1: Study Design

V	1	V2	V3	V4	V5	V6	Phone FU
- 1		Baseline					
	Week -4 to -1	Day 0 Study Drug	Day 1	Week 1	Week Z	Week 4	Week 8
	Screening	Administration Single 6-hour IV Infusion dose of 120mg/m ²			Follow-up		

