5.3 Strategies for Recruitment and Retention

One challenge in studying rare diseases is the feasibility of recruitment. We have established relationships with more than 90 families through the Developmental Synaptopathies Consortium (DSC) as part of the Rare Disease Clinical Research Network across six sites. Approximately 40 percent of these children are expected to

have seizures and should meet inclusion criteria. Intractable epilepsy is a frequently discussed issue in parent online forums and we are confident that the first clinical trial specifically geared to address seizures will attract enormous interest, especially among the most severely affected families. Should recruitment difficulties arise, we have collaborated with the national Phelan-McDermid Syndrome Foundation that has an international membership of approximately 1200 families, approximately 10 percent of whom live in the Northeast US. The PMSF has been a close partner on all our studies in PMS, enable successful recruitment of the DSC, and believes epilepsy to be a critical area that is currently understudied and where treatment is poorly understood. Likewise, we are confident that the interest in this area will ensure adequate retention for follow-up visits after the initial infusion.

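### The CGI-I User's Guide sets the threshold for a 2 by the clinician's confidence that the treatment is helping, although the form asks for total change whatever its cause

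*Combined protocol and SAP*

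**What the plan says.** Appendix C instructs the CGI-I rater in four places.

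- **Introduction to the CGI-S and CGI-I.** The clinician rates total improvement since baseline, "whether or not the improvement is judged to be due entirely to the experimental treatment".
- **Rating form.** The instruction beside the scores is the same: "Rate his/her total improvement whether or not, in your judgement, it is due entirely to the study drug".
- **User's Guide, numbered anchor 2.** A 2 may be given for moderate improvement in one symptom area, especially if seen across settings, or for moderate improvement in several areas even if confined to one setting. Durability is to be weighed. The anchor does not mention the treatment.
- **User's Guide, N.B.** "A CGI-I of 2 is appropriate for definite, unequivocal improvement of a magnitude that makes the clinician confident that the treatment is helping".

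On design, section 4.1 states: "This is an open-label study to investigate the safety, tolerability and efficacy of a single 6-hour intravenous infusion of AMO-01". Section 10.6.1 gives masking as not applicable. Section 7.1.9 asks that, as far as possible, the same evaluator see the subject at each visit, and describes that evaluator eliciting comments from the subject or caregiver. No independent or masked CGI-I rater is described. Section 4.2.2 lists CGI-I among the secondary endpoints.

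**The concern.** A global improvement score should record how much the subject has changed. Whether the drug caused the change is for the design and analysis to answer. The form and the introduction respect that division and the N.B. does not: it defines the threshold for a 2 through the rater's confidence that the treatment works.

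In a masked, controlled trial such wording would matter less, because a rater's belief could not follow treatment assignment. Here every treated subject receives AMO-01, the rater knows it, and no comparison arm offsets expectation. A rating that depends partly on belief in the drug would then be counted as evidence of efficacy. The protocol must accept some expectation bias because of its design, but its rating instructions need not add to it.

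**Working it through.** The plan states no figure on this point and the conclusion depends on none, so the check sets the instructions side by side and follows typical cases through them.

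**What each text makes the rater judge when considering a 2**

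| Text in Appendix C | Size and certainty of change | Areas, settings, durability | Belief about the drug |
|---|---|---|---|
| Introduction | total improvement | not addressed | need not be the sole cause |
| Form | total improvement | not addressed | need not be the sole cause |
| User's Guide, anchor 2 | moderate | yes | not mentioned |
| User's Guide, N.B. | definite, unequivocal | not addressed for a 2 | yes, sets the magnitude |

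Only the N.B. asks for a view on whether the treatment is helping. It is also the last guidance before the form, so a rater could reasonably use it to settle a doubtful case.

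**Case 1: moderate, definite, lasting improvement, credited to the drug.** The form, anchor 2 and the N.B. all lead to a 2. There is no conflict.

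**Case 2: the same improvement, credited to something else.** The form and anchor 2 still lead to a 2. The N.B. no longer clearly supports a 2, but it does not support a lower score either. It keeps a 3 for changes that are not definite and unequivocal, and a 4 for "slight variation in either direction of a magnitude that is likely due to chance, natural history, external events, or rating error". The text is awkward here, but it gives no route down to a 3 or 4.

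**Case 3: a change near the boundary of 2 and 3, seen by a rater who believes the drug works.** By size, breadth and durability, anchors 2 and 3 would make this a 3. The N.B. offers a further test, confidence that the treatment is helping, and this rater passes it. The same confidence can make an uncertain change look definite. Here the wording can raise a score, and it works in the drug's favour.

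**Size.** To quantify Case 3 one would need the number of ratings lying near that boundary and the probability that belief decides them. The documents give neither. Section 10.5 says the sample size had no statistical basis, so there is no assumed CGI-I effect to compare with. Sections 10.4 to 10.4.3 define no CGI-I responder cut-off. Appendix C mentions dividing subjects into responders and non-responders only as a convention. No numerical effect on a planned analysis can therefore be derived.

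**The case against.** The strongest defence is that the clause qualifies magnitude. It describes how large a change must be and need not mean that cause is being scored. The operative anchor for a 2 is sound, and section 7.1.9 lists the scores without attribution and provides standard prompts. The form disclaims only sole attribution to the drug, so confidence that treatment is helping does not flatly contradict it. Expectation bias comes from the open-label, uncontrolled design and would survive any rewording.

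Most of this is fair and limits the weight of the point. It does not remove it. A magnitude measured by confidence in the treatment still requires the rater to form a view about the treatment, which neither the form nor anchor 2 asks for. That the design already carries expectation bias is a reason not to write more of it into the instructions.

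The defence also rules out several stronger readings that a reader might draw:

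- **That a 1 depends on enthusiasm.** The guide says a 1 "is usually accompanied by considerable patient and/or caregiver enthusiasm". That is a usual accompaniment. The requirement is very substantial improvement.
- **That the 4 imports attribution in the drug's favour.** Its wording sets a noise threshold that applies equally to small gains and small losses.
- **That the absence of treatment wording for scores 5 to 7 shows a built-in tilt.** The N.B. treats 3 and 5 together, and the 4 is symmetric. The contrast is too partial to carry an argument.
- **That recruitment selects believers.** Section 5.3 predicts that the trial "will attract enormous interest, especially among the most severely affected families". This is a statement about feasibility and describes no targeting.

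**Conclusion.** The point holds in a narrow form. One sentence of live rater guidance introduces a treatment-belief criterion that the form and introduction leave out and that goes beyond the guide's own anchor 2. The likely direction is upward, from a 3 to a 2, for borderline changes seen by a rater who believes in the drug. This is an inference from the wording and the unmasked design. The documents do not show that any rating would be affected.

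A reader might infer that a definite improvement would drop from 2 to 3 or 4 when credited to another cause, and convert that into a shift in the mean or in the share rated much improved. The documents do not support this. The N.B.'s own definitions of 3 and 4 exclude a definite improvement, and no such share is a planned analysis.

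The frequency of the effect is unknown. CGI-I is one of nine secondary endpoints, the study describes itself as exploratory proof of concept, and its primary endpoints are safety. The priority is minor: a free improvement to make when Appendix C is next revised.

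**What to change.** Replace the N.B. sentence on a score of 2 with: *A CGI-I of 2 is appropriate for definite, unequivocal improvement of the size, breadth and durability described in anchor 2, whatever its cause.* Remind raters that the form's instruction to score total change governs every rating. Anchors 1 and 4 need no change on this account.

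The cost is one sentence in Appendix C and a short note to raters, with no added data, visits or staff. If ratings have already been made under the present wording, record the date of the change and state in the report which ratings came before it. The edit will not remove the expectation bias of an open-label, single-arm design, so CGI-I results should still be read with that in mind.
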